10.4.8 Multiple Comparison/Multiplicity

N/A

10.4.9 Tabulation of Individual Response Data

Reports of ocular pain will be tabulated by treatment group, by number of patients reporting ocular pain as either “No Pain” or “Pain” (trace to severe) at each follow-up visit (Visit 4 through Visit 7).

10.4.10 Exploratory Analyses

N/A

10.5 Sample Size

Since this is a pilot study, no formal sample size estimation was performed.

10.6 Measures to Minimize Bias

To minimize bias, the study has been designed as a randomized, double blind study.

10.6.1 Enrollment/ Randomization/Masking Procedures

Randomization will be stratified (or balanced) by study center. Patients will be randomized in a ratio of 2:1, 2 active (N-PPDS) for each placebo (p-PPDS). Treatment assignments for this study have been randomized in blocks of three (each sequential group of three, two lines are active treatment, and one line is placebo treatment), 25 blocks total. Using a random number generator (JMP 10.0 statistical software), each block is assigned three randomized numbers. The dataset is then sorted by ascending order by block, by random number. By ascending order, each line is assigned a subject number (e.g. 101-175). As a subject qualifies for enrollment, they will be sequentially assigned a subject number. The subject numbers designated what treatment group the subject will be assigned.

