Study Subject	An individual that has signed a HIPAA form and an IRB approved study consent form
Subject	Individual being considered for enrollment in to the study
UP	Unanticipated Problem

STUDY SYNOPSIS

Title: A clinical study evaluating the safety and efficacy of punctal plug delivery system (Evolute®) of Nepafenac (N-PPDS) compared with a Placebo Punctal Plug Delivery System (p-PPDS) in Controlling Post-Operative Ocular Pain and inflammation in Subjects undergoing Routine Unilateral Cataract Surgery

Sponsor: Mati Therapeutics Inc.

Clinical Phase: 2

Investigational Masked Product: N-PPDS (Nepafenac Punctal Plug Deliver System) is an L-shaped, silicone punctal plug with a drug eluting core that contains nepafenac (active)

Comparator Masked Product: p-PPDS (placebo Punctal Plug Delivery System) is an L-shaped, silicone punctal plug with a drug insert that contains no active ingredient (placebo).

Number of Sites: up to 3 sites in the USA.

Study Population: Approximately 75 qualified subjects (75 eyes) who have given written consent, have met all study inclusion/exclusion criteria and are scheduled to undergo unilateral cataract surgery with the implantation of an intraocular lens (IOL) will be enrolled in to the study.

Study Objectives: To evaluate the safety and ocular efficacy of N-PPDS in controlling post-operative ocular pain and inflammation associated with cataract surgery.

Study Design: This is a Phase 2, multi-center, randomized, parallel-arm, double-masked, placebo-controlled study. One (1) to 2 days prior to their scheduled cataract surgery, each study subject will be randomized (2:1) in to one of two treatment groups:

Group A: A total of 50 study subjects (50 eyes) will have an N-PPDS inserted in the lower punctum of their scheduled surgical eye.

Group B: A total of 25 study subjects (25 eyes) will have a p-PPDS inserted in the lower punctum of their scheduled surgical eye.

All plugs will remain in the study subject's lower punctum for a period of 2 weeks following cataract surgery.

Subject Selection: The following are inclusion and exclusion criteria for a prospective study subject:

Study Inclusion Criteria:

1. A male or female subject in good general health, ≥ 22 years of age at the time of the screening visit
2. A patient must be able to read, comprehend and willing to give HIPAA & informed consent.

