4.2 Study Endpoints

The study will be complete when 75 study subjects (75 eyes) have been evaluated at Visit 7 (Day 14 post-op) or have been terminated from the study.

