6.1 Study Treatments

6.1.1 Route of Administration

Each qualified study subject as they are enrolled in to the study will be sequentially assigned a Subject ID number. Treatment assignments for this study have been randomized (see [Section 10.6.1](#) for details on treatment randomization) to determine which one of the two masked punctal plug drug delivery systems a study subject will receive for the duration of the study.

[figure not shown]

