11.3 Subject Confidentiality

Records identifying the study subject by name will be kept confidential. The Investigator will ensure the study subject's anonymity is maintained throughout the course of the study. A study subject will be assigned a site/subject ID number to maintain study subject confidentiality. In particular, the Investigator will keep an enrollment log with confidential identifying information that corresponds to the subject numbers and initials of each study subject. A study subject name may possibly be disclosed to Mati Therapeutics Inc. or regulatory agencies during inspection of medical records related to the study, but reasonable precautions will be taken to maintain confidentiality of personal information to the extent permitted by applicable laws and regulations. If the results of the study are published, the study subject's identity will remain confidential.

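### Randomisation is stratified by center but no efficacy analysis uses center, and the protocol contradicts itself on whether subjects with surgical complications are replaced

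*Combined protocol and SAP*

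**What the plan says.** **Randomisation and analysis.** Section 10.6.1 promises that "Randomization will be stratified (or balanced) by study center". The Synopsis plans "up to 3 sites in the USA". Section 10.3 pools data across centers unless something else is specified, and sections 10.4.2, 10.4.3 and 10.4.7 specify nothing by center. Sections 10.4.2 and 10.4.3 name variables and data sets but no efficacy test. Section 10.4.1 sets two-sided tests at 5%. Section 10.4.9 tabulates pain as none versus any, by group and visit.

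**Disposition after a surgical complication.** Section 5.3 says such a subject is discontinued and points to 5.5.2.2; section 5.5.1.2 also lists the complication as a reason for discontinuation. Under 5.5.2.2 discontinued subjects are replaced. Section 7.4.3 says that a subject with any complication listed in 5.3 is terminated. Under 5.5.2.1 terminated subjects count as having completed and are not replaced. Section 4.2 sets the end of the study: "The study will be complete when 75 study subjects (75 eyes) have been evaluated at Visit 7 (Day 14 post-op) or have been terminated" from it.

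**The list.** Section 10.6.1 describes blocks in which "each sequential group of three, two lines are active treatment, and one line is placebo treatment), 25 blocks total". It continues: "By ascending order, each line is assigned a subject number (e.g. 101-175"), and "As a subject qualifies for enrollment, they will be sequentially assigned a subject number". Section 11.3 adds that "A study subject will be assigned a site/subject ID number", without linking this to the list.

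**The concern.** A design that balances treatment within center removes between-center variation from the treatment difference. A pooled test still counts that variation as noise. If centers differ in outcome, the test is too cautious under the null hypothesis and less powerful under the alternative. Nothing in 10.3 or 10.4 suggests that leaving center out was a considered choice.

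The disposition conflict matters because it decides who is replaced, who counts toward the 75 that close the study, and how many assignments are used. It may also affect follow-up, since section 5.5 follows terminated subjects through Day 14 or until the condition has resolved or stabilised.

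The list description matters less, but 10.6.1 is where a reader must be able to confirm that the promised center balance is delivered and see where a replacement's assignment comes from.

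**Working it through.** **1. The plan's own figure.** 25 blocks × 3 = 75 lines; 25 × 2 = 50 active and 25 × 1 = 25 placebo. This reproduces the planned 50 and 25 and leaves no spare line.

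**2. What pooling can cost (illustrative).**
- From the documents: 50 versus 25 subjects; up to three centers; two-sided 5%; Day 1 pain-free rates of about 50% on vehicle and 80% on nepafenac 0.1% drops (section 2.1).
- Assumed: a Day 1 comparison of no pain with pain; true stratification in 8, 8 and 9 blocks (24, 24 and 27 subjects); a common odds ratio of (0.80/0.20)/(0.50/0.50) = 4; placebo pain-free rates by center as in the table.
- Pooled test: X² = (A − E)²/V, where A is the number pain-free on active, E = n₁M/T and V = n₁n₀M(T − M)/T³. M is the total pain-free and T = 75.
- Cochran-Mantel-Haenszel (CMH): (Σ(aₖ − Eₖ))²/ΣVₖ, with Vₖ = n₁ₖn₀ₖmₖ(Nₖ − mₖ)/(Nₖ²(Nₖ − 1)) in center k.
- 40,000 simulated trials per case.

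| Placebo pain-free by center | Pooled chi-square power | CMH power |
|---|---|---|
| 20/50/80% | 58% | 66% |
| 30/50/70% | 70% | 72% |
| 40/50/60% | 75% | 75% |
| 50/50/50% | 76.4% | 75.5% |

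With unequal centers (13/8/4 blocks) at 20/50/80% the figures are 66% and 71%. With two centers they are 47% and 61% at 20/80%, 67% and 70% at 30/70%, and 75% and 75% at 40/60%.

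**3. Type I error.** At 20/50/80% the pooled test rejects a true null in 3.0% of trials and CMH in about 4.9%. A hand check gives the direction. The pooled variance uses 0.5 × 0.5 = 0.25, while the average within-center variance is (0.16 + 0.25 + 0.16)/3 = 0.19. The ratio is 0.76, so the effective critical value is 1.96/√0.76 = 2.25, a two-sided level of about 2.5%. With no center difference the pooled chi-square runs at 6.1%. That excess belongs to the uncorrected chi-square at 50 versus 25: the single-stratum Mantel-Haenszel form of the pooled test runs at 5.1% with 74.7% power. Against that form, CMH loses nothing.

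**4. Disposition, side by side.** Let k subjects have a listed complication.

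| Passage | Status | Replaced? | Counts toward the 75 in 4.2? | Randomised, k counted alone |
|---|---|---|---|---|
| 5.3, 5.5.1.2 with 5.5.2.2 | Discontinued | Yes | Not unless evaluated at Visit 7 | 75 + k |
| 7.4.3 with 5.5.2.1 | Terminated | No | Yes | 75 |

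No complication rate is given. At an assumed 2% to 10%, k is about 75 × 0.02 = 1.5 to 75 × 0.10 = 7.5. (The 75 + k column does not count replacements who themselves have a complication.)

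**5. Spare lines.** No replacement rate is given. The chance that at least one of 75 subjects is replaced is 1 − (1 − d)⁷⁵: 53%, 78% and 98% at assumed rates d of 1%, 2% and 5%. Some demand beyond line 75 is therefore likely if there is one 75-line list.

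**The case against.** The case against is substantial, and most of it stands.

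- **Center in the analysis is a matter of precision.** The unadjusted comparison is unbiased, pooling is a stated choice, no passage shows center differences, and section 10.5 calls this a pilot, so no power target is missed. At modest differences (40/50/60%) CMH gains nothing. All of this stands. What remains is that the stratified test costs about 1 point at worst and holds its level whether or not centers differ.
- **A reader might infer that stratification fails.** The documents do not support this. Section 10.6.1 states the rule. Whole blocks shared out to centers would honour it, and so would a 75-line list per center, which the example numbering and the site/subject identifier in 11.3 would allow. Imbalance figures for one list running across sites would describe an arrangement that the section's first sentence excludes.
- **A reader might infer that replacements have no assignment rule.** They do have one: a replacement is a newly qualifying subject and takes the next sequential number, and the same program can generate more blocks. Only the list length and its tie to center are unstated.
- **A reader might want a fixed longer list.** Pooled totals for a 95% chance of 75 non-replaced subjects are 84, 90, 96 and 102 lines in whole blocks at assumed replacement rates of 5, 10, 15 and 20%. They do not suit center-specific lists: three centers that must each reach 25 would jointly need 90, 99, 108 and 117. No document figure favours any rate, and an extendable list removes the need to choose. Claims that shared blocks would run out even without replacement depend on assuming free enrolment, which the documents do not state.

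**Conclusion.** The point holds as two low-cost improvements and one clarification.

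1. Center is a stratification factor that the efficacy analysis ignores. There is no bias. In the illustration, the loss with three near-equal centers runs from none to about 8 points of power, the latter only if centers differ as widely as 20/50/80%; type I error there falls to 3.0%. This rests on an assumed test, effect and center pattern. The absence of any named efficacy test is a wider gap and is not counted here.
2. The disposition passages contradict each other on surgical complications. This needs no assumption. Its numerical effect is one assignment and one place in the count of 75 for each affected subject.
3. The missing mapping of blocks to centers and the absence of spare lines are gaps in description. They are not evidence that allocation would be unbalanced or improvised.

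**What to change.** - **Sections 10.3 and 10.4.2 to 10.4.3.** When the efficacy tests are named, make them center-stratified: Cochran-Mantel-Haenszel for no pain versus pain, van Elteren for ordinal severity, or center as a model factor. Cost: a sentence or two, and about 1 point of power against the uncorrected chi-square if centers do not differ.
- **Sections 5.3, 5.5.1.2 and 7.4.3.** Reconcile the status of subjects with surgical complications, so that replacement under 5.5.2 and the count in 4.2 follow without ambiguity. Which status applies is for the sponsor to decide. Cost: one wording change.
- **Section 10.6.1.** State that each center has its own blocked 2:1 list, produced before enrolment and extendable by the same program before it runs out. State also that a replacement takes the next unused number at that center and is never matched to the arm of the subject replaced. If separate 75-line lists per center are already intended, say so. Cost: a short paragraph and, if needed, a few more blocks. No fixed list length is required.

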7.9.1 Administration of a Rescue Medication

Following cataract surgery, a rescue treatment with an ocular topical corticosteroid (prednisolone acetate 1% q.i.d.) should be administered in the study eye, at the discretion of the physician, if any of the following rescue criteria apply:

- a. Anterior Chamber Cell grade is 3 (grade 3 = 16-30+ cells) or greater
- b. Anterior Chamber Flare grade is 3 (grade 3 = moderate intensity) or greater
- c. Subject reports moderate to severe ocular pain

A study subject will be followed through Visit 7 (Day 14) or until the study subject's post-op ocular pain and/or inflammation in the study eye has resolved or has become medically stable. The use of a rescue medication during the study will be documented on the Concomitant Medication CRF.

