8.7.5 Unmasking Study Treatment

Masked information on the identity of the assigned test article will be provided for each study subject. If the treatment code needs to be broken in the interest of the study subject's safety, the Investigator is encouraged to contact the Medical Monitor prior to unmasking if there is sufficient time. Dependent upon the individual circumstances (i.e., medical emergency), the individual code may be broken prior to contact with the Medical Monitor. The Medical Monitor must be informed in all cases in which the code was broken and of the circumstances involved.

The Medical Monitor for this study is: [name]
[contact] (office)
[contact] (cell)

Additionally, the Medical Monitor may be required to unmask a study subject's masked treatment if the AE meets criteria of a Suspected Unexpected Serious Adverse Reaction (SUSAR) in order to fulfill expedited regulatory reporting requirements.

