10.4.7 Planned Interim Analyses

An interim analysis will be performed to confirm that positive efficacy trends are being observed and that the enrolment should continue. The interim analysis will be performed after a minimum of 25 subjects have completed visit 7 in the study. The data will be unmasked and analysis of primary and secondary endpoints will be completed along with baseline descriptive statistics.

Sites will remain masked to treatment for the remainder of the study. A summary of the results may be shared with the sites but no individual site data will be generated or shared.

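### Fixed 2:1 blocks of three, disclosed in the protocol that sites hold, let one unmasked placebo subject reveal both block-mates if whole blocks are allotted to centres

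*Combined protocol and SAP*

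**What the plan says.** Section 10.6.1 stratifies randomization by centre at 2:1 and states that "Treatment assignments for this study have been randomized in blocks of three". It gives the content of a block ("each sequential group of three, two lines are active treatment, and one line is placebo treatment") and the number of blocks ("25 blocks total"). Lines are sorted by block, numbered consecutively (the example is 101 to 175), and assigned in sequence as subjects qualify. No variation in block size is described, and nothing is withheld from sites. Section 11.4 refers to investigators who have signed the protocol, so they hold this text.

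Other relevant provisions:

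- **Code break.** Section 8.7.5 allows a site to unmask a subject for safety; in an emergency "the individual code may be broken prior to contact with the Medical Monitor".
- **Visible clinical course.** One criterion for rescue in Section 7.9.1 is "Subject reports moderate to severe ocular pain"; others are grade 3 or greater cells or flare.
- **Interim.** Section 10.4.7 says "The data will be unmasked and analysis of primary and secondary endpoints will be completed". Its next paragraph keeps sites masked and rules out generating or sharing individual site data.
- **Endpoints.** Pain is the subject's response, taken at interview and recorded by the investigator (Section 7.2.1 c) on a 0 to 5 scale (Appendix 3 D). Cells and flare are slit-lamp grades by the investigator, 0 to 4 (Appendix 2 B).
- **Check on masking.** Section 10.6.2 gives the evaluation of blinding success as not applicable.

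**The concern.** Blocking protects the 2:1 ratio, but a short fixed block whose size and content are published also lets a reader deduce allocations. A site that knows the numbers run in threes from the start of its list can work out where every block begins and ends. One confirmed placebo then settles the other two subjects in that block.

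Both efficacy endpoints pass through an investigator's judgement, and the protocol asks that the investigator who made each assessment on Day 1 make it at every later visit. Knowledge gained about a subject could therefore colour that subject's remaining grades, and also the decision to rescue, which Section 7.9.1 leaves to the physician. With 25 placebo subjects planned, a few shifted grades would be noticeable, and no assessment of masking is planned that might reveal it.

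**Working it through.** **Inputs.** From Section 10.6.1: block size 3, content two active (A) and one placebo (P), 25 blocks, consecutive numbering. From Section 4.1: 50 active, 25 placebo. From Section 2.1 and Appendix 5: the topical nepafenac response rates used in step 4. The comparison schemes (blocks of six; a random mix of 3 and 6) are my assumption.

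**1. The plan's own figures.** 25 × 3 = 75; 25 × 2 = 50 active; 25 × 1 = 25 placebo. Numbers 101 to 175 are 75 numbers, exactly 25 threes. All agree with Section 4.1.

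**2. What one known allocation reveals, block boundaries known.** The possible orders are PAA, APA and AAP, equally likely.

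- One placebo known: each block-mate is active with probability 1.
- One active known: a given block-mate is placebo with probability 1/2, up from 1/3. Nothing is certain.
- Two actives known: the third is placebo with probability 1.

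For comparison, with one placebo known in a fixed block of six (4A, 2P), each block-mate is active with probability 4/5. If the next subject in sequence is considered and boundaries are not known, the probability that this subject is active is 8/9 for fixed threes and 22/27 = 0.815 for an equal mix of 3 and 6. With no information it is 2/3.

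**3. Ceiling: all earlier allocations in the block known.** An allocation is certain in advance once only one treatment remains in the block, so the number certain is the length of the final run of like letters.

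- Threes: PAA gives 2, APA 1, AAP 1. Mean 4/3 per block; (4/3)/3 = 4/9 = 44.4%, or 33.3 of 75.
- Sixes: over the 15 orders, final runs of A total 4 + 6 + 6 + 4 = 20 and final runs of P total 2 + 4 = 6. Mean 26/15; (26/15)/6 = 28.9%, or 21.7 of 75.
- Random 3 and 6, order undisclosed: simulated sequences of 24 subjects, updating the probability of each possible position in a block. With an equal mix, 9.6% are certain; the range is about 7% to 12% when one size is twice as frequent as the other.

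**4. What clinical course reveals.** I assume that the topical figures carry over to the plug and that lack of response stands in for rescue. With a the non-response rate on active and b that on vehicle, under 2:1 allocation P(placebo | non-response) = b/(b + 2a). A block-mate is then active with probability (1 + p)/2, where p is that result.

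| Non-response | a | b | P(placebo) | P(block-mate active) |
|---|---|---|---|---|
| Day 1 pain, 0.1% trials | 0.20 | 0.50 | 56% | 78% |
| Day 14 pain, 0.3% study 1 | 0.14 | 0.54 | 66% | 83% |
| Day 14 pain, 0.3% study 2 | 0.16 | 0.62 | 66% | 83% |
| Day 14 inflammation, study 1 | 0.35 | 0.68 | 49% | 75% |
| Day 14 inflammation, study 2 | 0.39 | 0.76 | 49% | 75% |

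The block adds some information when outcomes are read together. If one subject still has pain on Day 14 and both block-mates are pain-free, the chance that the first is placebo rises from 66% to 78-81%. Study 1: 0.54 × 0.86² = 0.399 against 2 × 0.14 × 0.46 × 0.86 = 0.111, so 0.399/0.510 = 78%. Study 2: 0.62 × 0.84² = 0.437 against 2 × 0.16 × 0.38 × 0.84 = 0.102, so 0.437/0.540 = 81%. Each block-mate's chance of being active rises from 79-82%, on that subject's own pain-free status alone, to 89-91%. No allocation becomes certain by this route.

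**The case against.** The best defence is that the scheme matters only if an allocation leaks, and the plan closes most leaks. Both plugs use the same plug component and excipients and are supplied masked (Section 6.1.2, Appendix 6). Emergency code breaks are exceptions; the plan gives no expected number. If a break is unrelated to arm, two in three reveal an active subject, which makes nothing certain. Pain is also the answer of a subject who is masked, which limits what an informed interviewer could change. All of this stands and keeps the point small. It does not answer why block size and content need to be in the site-facing text.

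Four stronger readings are tempting and are not supported:

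- **The interim exposes block-mates to sites.** A reader might infer this from the unmasking of at least 25 subjects. Section 10.4.7 says sites stay masked and allows at most a summary of results to reach them.
- **Each rescue exposes the block.** Step 4 shows a shift in probability, not identification.
- **44% of allocations will be known.** That figure requires every earlier allocation in each block to be known, and no route in the plan gives that. The 29% and 9-10% figures rest on the same premise.
- **The investigator can readily choose the next subject's arm.** Eligibility is assessed and surgery scheduled at Visit 1, whereas randomization is at Visit 2, which leaves limited room for it.

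Nor does the plan require one person to make both the pain and the slit-lamp assessments; it asks for consistency across visits within each.

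**Conclusion.** The concern holds as a weakness in concealment, not as evidence that masking will fail. A code break on one placebo subject turns one known allocation into three. Other signals available to a site only shift probabilities.

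The conclusion rests on two assumptions. First, block boundaries must be known; consecutive numbering in threes supplies them. Second, block-mates must be at the same site. Stratification by centre implies whole blocks per centre, but the single example series does not show how 25 blocks are divided among up to three sites. If sites draw from one shared list, block-mates may be elsewhere and the leak within a site is smaller.

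This is a cheap improvement, worth making because the endpoints are investigator-recorded and the remedy is simple.

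**What to change.** Regenerate the list within centre using randomly ordered blocks of 3 and 6. The section says assignments have already been randomized, so if enrolment has begun, apply this only to unused numbers. Remove the block size, block content and construction details from Section 10.6.1, keeping only the 2:1 ratio and the stratification by centre, and hold the rest in a restricted randomisation file.

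The cost is a few lines of code and a minor protocol amendment, with IRB approval unless it is classed as administrative (Section 7.1). Plug supplies must be re-matched if they are already numbered, which the documents do not say. Balance around 2:1 may be slightly looser at a small centre. Endpoints, sample size and clinical management are unaffected.
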